### 5.3.3. Analysis Methods

The testing of these secondary efficacy endpoints will be based on the stratified log rank test. Secondary efficacy endpoints will be summarized using the Kaplan-Meier method and displayed graphically where appropriate. Cox proportional hazard models will be used to estimate the HR and its 95% confidence interval.

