Attachment 2: ECOG PS Grade Scale**ECOG Grade Scale (with Karnofsky conversion)**

- | | |
|---|---|
| 0 | Fully active, able to carry on all predisease performance without restriction. (Karnofsky 90-100) |
| 1 | Restricted in physically strenuous activity but ambulatory and able to carry out work on a light or sedentary nature, eg, light housework, office work. (Karnofsky 70-80) |
| 2 | Ambulatory and capable of all self-care but unable to carry out any work activities. Up and about more than 50% of waking hours. (Karnofsky 50-60) |
| 3 | Capable of only limited self-care; confined to bed or chair more than 50% of waking hours. (Karnofsky 30-40) |
| 4 | Completely disabled. Cannot carry on any self-care. Totally confined to bed or chair. (Karnofsky 10-20) |
| 5 | Dead. (Karnofsky 0) |

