#### 5.3.1. Definition

- Time to pain progression is defined as the time from the date of randomization to the date of the first observation of pain progression. Pain progression is defined as an average increase by 2 points from

baseline to  $>4$  in the BPI-SF worst pain intensity (item 3) with no decrease in opioids confirmed  $\geq 3$  weeks apart or initiation of chronic opioids (see definition below), whichever occurs first. Subjects who did not experience pain progression at the time of the analysis will be censored on the last known date with no pain progression. Sensitivity analyses may be performed where increase of pain score to  $>4$  is not required, or confirmation is not required.

- Time to SRE is defined as the time from the date of randomization to the date of the first observation of an SRE. An SRE is defined as the occurrence of symptomatic pathological fracture, or spinal cord compression, or radiation to bone, or surgery to bone. Subjects who did not experience an SRE at the time of the analysis will be censored on the last known date with no SRE.
- Time to chronic opioid use is defined as the time from date of randomization to the first date of confirmed chronic opioid use. For subjects entering the study without receiving opioids, chronic opioid use is defined as administration of opioid analgesics lasting for  $\geq 3$  weeks for oral or  $\geq 7$  days for non-oral formulations. For subjects entering the study already receiving opioids, chronic opioid use is defined as a  $\geq 30\%$  increase in total daily dose of the opioid analgesics lasting for  $\geq 3$  weeks for oral or  $\geq 7$  days for non-oral formulations. Subjects with no chronic opioid use at the time of the analysis will be censored on the last known date with no chronic opioid use.
- Time to initiation of cytotoxic chemotherapy is defined as the time from the date of randomization to the date of initiation of cytotoxic chemotherapy. Subjects who did not initiate cytotoxic chemotherapy at the time of the analysis will be censored on the last known date with no cytotoxic chemotherapy.

If there is heavy censoring due to death for some secondary endpoints, sensitivity analyses counting death as event may be performed if deemed clinically meaningful.

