**Table 3: Other Endpoints**

Endpoint	Description	Analysis Population
Patient Reported Outcomes and Analgesics Use	
The patient-reported outcomes will include the following:
 
 
• FACT-P: FACT-P total score, each subscale score (PWB, SFWB, EWB, FWB, FACT-G, PCS), and TOI.
 
• BPI-SF: 4 pain severity items (worst, least, average and now) and 7 pain interference items
 
• BFI: 3 severity items (now, usual and worst) and 6 fatigue interference items
 
• EQ-5D-5L: 5 domains and EQ visual analogue scale (VAS)
 
• Analgesics use
 
 
See Section 5.5.3 for detailed description of endpoints and analysis.
	PRO Population
Time to symptomatic local progression	The time from randomization to the date of the first occurrence of urethral obstruction or bladder outlet obstruction. Subjects with no symptomatic local progression at the time of analysis will be censored on the last known date the subject was known to have not progressed.	ITT Population
Time to PSA progression	The time from the date of randomization to the date of PSA progression based on Prostate Cancer Working Group 2 (PCWG2) criteria.  Subjects with no PSA progression at the time of analysis will be censored on the last known date with no PSA progression.	ITT Population
Prostate cancer-specific survival	The time from randomization to the date of death from prostate cancer-specific cause. Subjects alive at time of analysis will be censored on the last date the subject was known to be alive or lost to follow-up. Subjects who die from other than prostate cancer-specific causes at time of analysis will be censored on the death date.	ITT Population

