**Table 3: Other Endpoints**

Endpoint	Description	Analysis Population
PFS2	The time from date of randomization to date of disease progression on the first subsequent therapy for prostate cancer or death, whichever occurs first. Subjects with no disease progression on the first subsequent therapy will be censored on the last known date the subject was known to have not progressed. Subjects not on subsequent therapy will be censored on the last known date of no progression.	ITT Population
Time to ECOG PS deterioration	The time from the date of randomization to the first date of deterioration in ECOG PS (defined as the worsening of ECOG PS grade by at least one point). Subjects who have no deterioration in ECOG PS grade at the time of analysis will be censored at the last known date of no deterioration. Subjects with no on-study assessment or no baseline assessment will be censored at date of randomization.	ITT Population

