### 5.5.2. Analysis Methods

Analyses of the other endpoints will be performed on the ITT population, unless otherwise specified. Analysis of time-to-event endpoints and endpoints with binary outcome will be carried out as described above (see start of Section 5).

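### Add cumulative incidence curves for the four secondary endpoints and prostate-cancer-specific survival: Kaplan-Meier with deaths censored overstates the share of men with the event, modestly at 24 months

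*SAP*

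**What the plan says.** The secondary endpoints are time to pain progression, skeletal-related event (SRE), chronic opioid use and cytotoxic chemotherapy. SAP 5.3.1 includes death in none of them. Men without the event are censored at the last date known to be free of it. For SRE the wording is "Subjects who did not experience an SRE at the time of the analysis will be censored on the last known date with no SRE", and the other three follow the same pattern. The same section confirms that deaths are handled as censoring: "If there is heavy censoring due to death for some secondary endpoints, sensitivity analyses counting death as event may be performed". That analysis is optional and has no defined trigger.

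SAP 5.3.3 gives the summary method: "Secondary efficacy endpoints will be summarized using the Kaplan-Meier method and displayed graphically where appropriate". Testing is by stratified log-rank, and the hazard ratio comes from a Cox model.

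For prostate-cancer-specific survival, SAP Table 3 says: "Subjects who die from other than prostate cancer-specific causes at time of analysis will be censored on the death date". SAP 5.5.2 refers back for the method ("Analysis of time-to-event endpoints and endpoints with binary outcome will be carried out as described above"), and the start of SAP Section 5 names Kaplan-Meier with median event times.

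Neither document plans a cumulative incidence estimate for any of these five endpoints.

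**The concern.** Kaplan-Meier treats a censored man as still able to have the event later. A man who has died cannot. One minus Kaplan-Meier therefore estimates the risk in a setting where nobody dies first, and it exceeds the actual share whenever some men do die first. The composite in SAP 5.3.1 does not correct this. It estimates the share of men who have the event or die, and it does not extend to prostate-cancer-specific survival.

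What is at stake is the reading of absolute risk. Clinicians tend to read these curves as the proportion of men who will need opioids or chemotherapy. SAP Attachment 1 also uses Kaplan-Meier distributions of pain progression, opioid use and chemotherapy by arm for health-economic work, where absolute probabilities matter. In addition, SAP Section 5 says that if proportional hazards fails, the median in each arm becomes the only effect estimate. The excess grows with mortality, so it differs between arms if apalutamide prolongs survival.

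**Working it through.** **1. Death rate in the plan.** SAP 1.4 gives a 44-month control median for overall survival (OS), a hazard ratio of 0.75, about 1,000 men randomised 1:1, 30 months of accrual and 410 deaths at about 54 months. With exponential survival, the monthly hazards are:
- control: ln 2 / 44 = 0.01575
- apalutamide: 0.75 × 0.01575 = 0.01182

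With uniform accrual over A = 30 months and no dropout (assumed), expected deaths per arm at study month T ≥ A are

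500 × {1 − [exp(−λ(T − A)) − exp(−λT)] / (λA)}.

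At T = 54 this gives 227.0 + 183.0 = 409.9 (before rounding), which reproduces the plan's 410. The death hazards used below are therefore the plan's own.

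**2. When the curves are read.** Protocol 11.3.3 and SAP 5.3 place the secondary analysis at the first OS interim, about 205 deaths. The same formula gives 115.1 + 89.8 = 204.9 deaths at month 32.2. Potential follow-up then runs from about 2 to 32 months. Nobody reaches 36 months, and (32.2 − 24) / 30 = 27% of men could have more than 24. Hence 24 months is the main time point here.

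**3. Formulas.** With constant event hazard e and constant hazard d of death before the event:
- one minus Kaplan-Meier: 1 − exp(−e·t)
- cumulative incidence: e / (e + d) × {1 − exp[−(e + d)·t]}

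**4. Secondary endpoints, control arm, 24 months.** The documents give no event rates and no rate of death before the event, so both are assumed over a range: e = 0.005, 0.01 or 0.02 per month, and d = 25%, 50% or 100% of 0.01575. The 100% case is in effect an upper limit. It lets event-free men die at the full overall rate, although some deaths will follow pain progression, SRE, opioids or chemotherapy.

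| e per month | 1 − KM | Cumulative incidence at 25 / 50 / 100% | Overstatement, points |
|---|---|---|---|
| 0.005 | 11.3% | 10.8 / 10.3 / 9.5% | 0.5 / 1.0 / 1.9 |
| 0.01 | 21.3% | 20.4 / 19.5 / 17.9% | 0.9 / 1.8 / 3.4 |
| 0.02 | 38.1% | 36.5 / 35.0 / 32.2% | 1.6 / 3.1 / 5.9 |

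Worked cell: e = 0.01, d = 0.01575. 1 − exp(−0.24) = 21.3%. Cumulative incidence = 0.01 / 0.02575 × [1 − exp(−0.618)] = 17.9%. The difference is 3.4 points.

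**5. Difference between arms.** Take the same e in both arms and 0.75 × d on apalutamide. For the worked cell, the apalutamide cumulative incidence is 18.7%, an excess of 2.7 points against 3.4 on control. Over the whole grid, the two arms' overstatements differ by 0.1 to 1.4 points at 24 months.

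**6. Prostate-cancer-specific survival.** The only cause-of-death split in the documents is in Protocol 1.2: 84% of control-arm deaths from prostate cancer in a cited multi-arm trial whose population was 61% metastatic. Applying that share here is an assumption. For control, e = 0.84 × 0.01575 = 0.01323 and d = 0.16 × 0.01575 = 0.00252.

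| Month | 1 − KM | Cumulative incidence | Overstatement, points |
|---|---|---|---|
| 24 | 27.2% | 26.4% | 0.8 |
| 36 | 37.9% | 36.4% | 1.5 |
| 54 | 51.1% | 48.1% | 2.9 |

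On apalutamide the excess is 0.45 points at 24 months and 1.9 at 54. If the share is varied from 70% to 95%, the control excess runs from 0.3 to 1.2 points at 24 months and from 1.0 to 4.8 at 54.

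**The case against.** **No inference depends on this.** Significance claims rest on the log-rank test, and censoring deaths is the correct construction for a cause-specific hazard. This stands. The point concerns description only.

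**The SAP has seen the issue.** It allows that "sensitivity analyses counting death as event may be performed if deemed clinically meaningful". This stands in part: the SAP recognises the problem, but its remedy is discretionary and estimates a composite.

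**Kaplan-Meier belongs with the hazard ratio.** It is the curve that matches the cause-specific test. Cumulative incidence also mixes the effect on the event with the effect on death, so a drug that prolongs life can raise the share of men who live long enough to have the event. This stands, and is the reason to add a curve and not to replace one. The plan also lists no landmark rates for these endpoints; its 2-year and 3-year rates are for OS only.

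**The effect may be small.** At low event rates, or if most deaths follow the event, the excess at 24 months is under 1 point. This stands as well. It limits the priority of the point but does not remove the direction of the bias.

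**Conclusion.** The reading of the method and the direction of the bias hold for all five endpoints. The size is modest: about 0.5 to 6 points at 24 months in the control arm for the secondary endpoints, and about 0.8 points at 24 months and 2.9 at 54 for prostate-cancer-specific survival. These figures rest on constant hazards, the plan's 44-month median, assumed event hazards, an assumed share of deaths that precede the event, and the 84% split from a cited trial. This is a cheap improvement in reporting.

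Three stronger readings are tempting, and the documents do not support them:
- **A distortion of 4 to 11 points, or several points for all five endpoints.** The same formulas give 3.8 to 10.8 points at 36 months, but only if event-free men die at the full overall rate, and at a horizon that the planned secondary analysis does not reach. Prostate-cancer-specific survival stays below 1 point at 24 months with the 84% share.
- **An invalid treatment comparison.** The test and the hazard ratio remain valid for the cause-specific hazard.
- **An error in time to ECOG PS deterioration, because Protocol Attachment 2 lists death as grade 5.** SAP Table 3 does not say how deaths are handled for that endpoint, and counting death as deterioration would be a debatable change of estimand. It is not part of this point.

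**What to change.** In SAP 5.3.3 and 5.5.2, add Aalen-Johansen cumulative incidence curves by arm as the absolute-risk summary for the four secondary endpoints, with death as the competing event, and for prostate-cancer-specific survival, with other-cause death as the competing event. Keep Kaplan-Meier, the stratified log-rank test and the Cox hazard ratio, and label them cause-specific.

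Dates of death are already collected for OS, and SAP Table 3 already requires the cause. No new data, alpha or sample size is needed. The cost is a little more analysis work, event shares that read slightly lower, and the need to read the curves alongside OS.

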## 5.4. Additional Analysis for OS Endpoint

The following sensitivity analyses for the OS may be carried out as appropriate if it is deemed useful to aid in the interpretation of the results.

### 5.4.1. Covariate Effects

Multivariate analysis of OS adjusting for baseline prognostic factors will be performed as outlined in Section 5.2.1.3. The results may be used to support the findings obtained from the primary analysis. In the event that some of the prognostic factors are not highly prognostic for this endpoint, additional exploratory analysis may be conducted by first examining each baseline factors in a univariate analysis. The factors with p-value  $\leq 0.05$  will be included in the multivariate model.

### 5.4.2. Subsequent Therapies

To assess the impact of the use of subsequent therapies on the treatment effect on the OS, a time-dependent analysis using Cox regression may be performed. A stratified Cox model will include treatment variable and a time-dependent covariate for the status change with respect to receiving

subsequent therapy. Stratified hazard ratio and its 95% confidence interval for treatment will be provided. This analysis may be conducted if a significant number of subjects receive subsequent therapies.

### 5.4.3. Crossover

In the event that a large number of subjects in the placebo group crossover to an AR signaling inhibitor, at least one of the following analyses may be used, if appropriate, in estimating the true treatment effect on OS:

- The rank preserving failure time model as described by Robins and Tsiatis
- Inverse Probability Censoring Weighted (IPCW) log-rank test as described by Cole and Hernan
- Iterative Parameter Estimate (IPE) method as described by Branson and Whitehead

## 5.5. Other Endpoints

### 5.5.1. Definition

Other endpoints are defined in the following table.

**Table 3: Other Endpoints**

Endpoint	Description	Analysis Population
Patient Reported Outcomes and Analgesics Use	
The patient-reported outcomes will include the following:
 
 
• FACT-P: FACT-P total score, each subscale score (PWB, SFWB, EWB, FWB, FACT-G, PCS), and TOI.
 
• BPI-SF: 4 pain severity items (worst, least, average and now) and 7 pain interference items
 
• BFI: 3 severity items (now, usual and worst) and 6 fatigue interference items
 
• EQ-5D-5L: 5 domains and EQ visual analogue scale (VAS)
 
• Analgesics use
 
 
See Section 5.5.3 for detailed description of endpoints and analysis.
	PRO Population
Time to symptomatic local progression	The time from randomization to the date of the first occurrence of urethral obstruction or bladder outlet obstruction. Subjects with no symptomatic local progression at the time of analysis will be censored on the last known date the subject was known to have not progressed.	ITT Population
Time to PSA progression	The time from the date of randomization to the date of PSA progression based on Prostate Cancer Working Group 2 (PCWG2) criteria.  Subjects with no PSA progression at the time of analysis will be censored on the last known date with no PSA progression.	ITT Population
Prostate cancer-specific survival	The time from randomization to the date of death from prostate cancer-specific cause. Subjects alive at time of analysis will be censored on the last date the subject was known to be alive or lost to follow-up. Subjects who die from other than prostate cancer-specific causes at time of analysis will be censored on the death date.	ITT Population

**Table 3: Other Endpoints**

Endpoint	Description	Analysis Population
PFS2	The time from date of randomization to date of disease progression on the first subsequent therapy for prostate cancer or death, whichever occurs first. Subjects with no disease progression on the first subsequent therapy will be censored on the last known date the subject was known to have not progressed. Subjects not on subsequent therapy will be censored on the last known date of no progression.	ITT Population
Time to ECOG PS deterioration	The time from the date of randomization to the first date of deterioration in ECOG PS (defined as the worsening of ECOG PS grade by at least one point). Subjects who have no deterioration in ECOG PS grade at the time of analysis will be censored at the last known date of no deterioration. Subjects with no on-study assessment or no baseline assessment will be censored at date of randomization.	ITT Population

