9.1.3. Treatment Phase

The Treatment Phase will begin at Cycle 1 Day 1 of treatment and will continue until study drug is discontinued. Subjects should start study drug within 3 calendar days after randomization. Visits for each cycle will have a ± 2 -day window except for CT/MRI and bone scans (imaging visits may occur up to 8 days before cycles). Study visits will be calculated from the Cycle 1 Day 1 date. Please refer to the Time and Events Schedule for treatment visits and assessments during the Treatment Phase. The last measurements taken on Day 1 of Cycle 1 before administration of study drug or at screening (whichever value was last) will be defined as the baseline values.

After the PRO questionnaires have been administered, a symptom-directed physical exam and laboratory testing scheduled for the same visit will be conducted. Adverse events and changes to concomitant medications will be recorded. Subjects will be evaluated throughout this phase for possible toxicities. Dose modifications for toxicity will be made as according to criteria described in Section 6.3.

During the Treatment Phase, investigators will review all clinical, laboratory and imaging data, and will use this information to make decisions about dose modification and study medication discontinuation. Clinical evaluations and laboratory studies may be repeated more frequently, if clinically indicated. The subject should refrain from taking study drugs on the morning of study visits designated for trough PK sampling until seen at the site. Treatment will continue until disease progression or the occurrence of unacceptable treatment-related toxicity. If the subject has radiographic progression without clinical progression and alternate therapy is not initiated, treatment may continue at the discretion of the investigator. Subjects must discontinue treatment if clinical progression is documented (see Section 10.2). Once the subject discontinues study drug, the subject will complete the End-of-Treatment (EOT) Visit.

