9.1.5. Follow-up Phase

The Follow-up Phase should begin once a subject discontinues study drug for any reason. During the Follow-up Phase information will be collected every 4 months until death, withdrawal of consent, lost to follow-up or termination of the study. The information collected during follow-up will include the following: survival, data on secondary endpoints (see Section 9.2.3), first subsequent therapy for prostate cancer, date and type of disease progression (radiographic, PSA, clinical or a combination) on the first subsequent systemic therapy for prostate cancer, and PROs (see Time and Events Schedule). Some follow-up information may be performed by telephone interview or chart review or other convenient methods, and will be reported on the eCRF.

During the Follow-up Phase, deaths regardless of causality and treatment-related SAEs will be collected and reported within 24 hours of discovery or notification of the event on the eCRF.

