Overall survival is defined as the time from date of randomization to date of death from any cause.

Secondary Endpoints

- Time to pain progression is defined as the time from the date of randomization to the date of the first observation of pain progression (see also Section [9.2.1](#))
- Time to SRE is defined as the time from the date of randomization to the date of the first observation of an SRE as defined in Section [9.2.1](#)
- Time to chronic opioid use is defined as the time from date of randomization to the first date of confirmed chronic opioid use (see also Section [10.2](#))
- Time to initiation of cytotoxic chemotherapy is defined as the time from date of randomization to the date of initiation of cytotoxic chemotherapy

Other Endpoints

- Time to symptomatic local progression such as urethral obstruction or bladder outlet obstruction, is defined as the time from date of randomization to date of symptomatic local progression, whichever occurs first

- Time to PSA progression is defined as the time from the date of randomization to the date of PSA progression based on PCWG2 criteria²⁹
- Explore response markers for apalutamide, AR gene anomalies and other markers previously shown to be responsible for resistance to apalutamide
- Prostate cancer-specific survival is defined as the time from randomization to the date of death if attributed to prostate cancer
- PFS2 is defined as the time from date of randomization to date of first occurrence of disease progression on first subsequent therapy for prostate cancer or death, whichever occurs first
- Time to ECOG PS grade deterioration is defined as the time from date of randomization to the first date of deterioration in ECOG PS grade (defined as the worsening of ECOG PS grade by at least 1 point)
- Change from baseline over time in each of the subscales of FACT-P, EQ-5D-5L VAS, BPI-SF interference subscale and BFI

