10.2. Discontinuation of Study Drug

If a subject's study drug must be discontinued before disease progression this will not result in automatic withdrawal of the subject from the study. If the subject has radiographic progression

without clinical progression and alternate therapy is not initiated, treatment may continue until clinical progression is observed. All attempts should be made to capture radiographic progression even in subjects who have evidence of clinical progression.

However, a subject's study treatment must be discontinued for:

- Clinical progression defined as:
 - Deterioration in ECOG PS grade to grade 3 or higher (related to prostate cancer progression)
 - Need to initiate any of the following because of tumor progression (even in the absence of radiographic evidence of disease)
 - Subsequent anti-cancer therapy for metastatic prostate cancer
 - Radiation therapy for metastatic prostate cancer lesion(s) (palliative radiation to lesions existing at baseline will not be considered clinical progression)
 - Surgical interventions for complications due to metastatic prostate cancer progression. (Note: Surgical interventions for complications of local-regional progression are not considered clinical progression)
 - Need for chronic opioid analgesics: For subjects entering the study without receiving opioids, chronic opioid use is defined as administration of opioid analgesics lasting for ≥ 3 weeks for oral or ≥ 7 days for non-oral formulations. For subjects entering the study already receiving opioids, chronic opioid use is defined as a $\geq 30\%$ increase in total daily dose of the opioid analgesics lasting for ≥ 3 weeks for oral or ≥ 7 days for non-oral formulations. NOTE: Administration of as needed (eg, not fixed or scheduled dosage) use of opioid analgesics or extended opioid use for treatment other than the subject's prostate cancer does not require discontinuation from study treatment (eg, codeine/acetaminophen combinations, hydrocodone/acetaminophen combinations, hydrocodone/ibuprofen combinations, oxycodone/acetaminophen combinations, oxycodone/aspirin combinations, tramadol)
- More than 2 dose level reductions for Grade 3 or higher treatment-related AEs (see [Table 1](#) and [Table 2](#))
- Seizure of any grade or Grade 4 neurotoxicity
- Subjects who have had their treatment assignment unblinded for any reason except for IDMC recommendation to unblind the study

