11.3. Efficacy Analyses

All continuous variables will be summarized using number of subjects (n), mean, standard deviation (SD), median, minimum, and maximum. Discrete variables will be summarized with n and percent. All efficacy endpoints will be analyzed using the ITT analysis set. Kaplan-Meier product limit method and Cox proportional hazards model will be used to estimate the time-to-event variables and to obtain the HR along with the associated confidence intervals. Unless otherwise specified, stratified log-rank test will be used to test the treatment effect for time-to-event variables. A subject without an event at the time of analysis will be censored at the last known date the subject did not have a documented radiographic progression. Detailed censoring rules will be provided in the Statistical Analysis Plan. Subgroup analysis will be performed based on data from subjects with low-volume and those with high-volume mHSPC. High-volume mHSPC is based on an adaptation of the CHARTED study and is defined as 1) visceral metastases and at least 1 bone lesion or 2) at least 4 bone lesions, with at least 1 bone lesion outside of the vertebral column or pelvis (see also Section 1.2).³² Low-volume mHSPC is defined as the presence of bone lesion(s) not meeting the definition of high-volume mHSPC.

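### PFS2: read most naturally, the SAP censors men alive after first progression without new therapy at a date before that progression, which is informative for this subset

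*SAP*

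**What the plan says.** The SAP (Table 3, Other Endpoints) defines PFS2 as "The time from date of randomization to date of disease progression on the first subsequent therapy for prostate cancer or death, whichever occurs first". Protocol 9.2.3 agrees: "PFS2 is defined as the time from date of randomization to date of first occurrence of disease progression on first subsequent therapy", or death. Table 3 then gives two censoring sentences.

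- Men on subsequent therapy, for whom the last date free of progression is used: "Subjects with no disease progression on the first subsequent therapy will be censored on the last known date the subject was known to have not" (final word omitted).
- Men without it: "Subjects not on subsequent therapy will be censored on the last known date of no progression".

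The second sentence does not say whether progression means first progression or the PFS2 progression.

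Three protocol statements bear on it.

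- Section 10.2 says that, for a subject with radiographic progression "without clinical progression and alternate therapy is not initiated, treatment may continue until clinical progression is observed". Section 9.1.3 has a matching provision.
- Section 9.1.5 covers the time after study drug stops: "During the Follow-up Phase information will be collected every 4 months until death, withdrawal of consent, lost to follow-up or termination of the study". The items collected include survival, the first subsequent therapy and progression on it.
- Section 11.3 has a general rule that a subject without an event "will be censored at the last known date the subject did not have a documented radiographic progression", with detailed rules left to the SAP.

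**The concern.** A man who has had his first progression, is alive and has not started another therapy has not had a PFS2 event. He is still at risk and still observed. If the second sentence refers to first progression, he leaves the risk set at a date before that progression, and his later event-free time is discarded. That time would have counted if he had died or had started new therapy. His censoring time therefore depends on his having progressed and on what happened to him afterwards, and censoring within each arm is no longer independent of outcome.

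What is at stake is the PFS2 estimate. SAP 5.5.2 sends time-to-event endpoints of this class to the stratified log-rank test and Cox model described at the start of Section 5, so a hazard ratio and p-value will be produced. Protocol 1.1.2.1 already reports such a PFS2 result for the earlier non-metastatic trial.

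**Working it through.** **Which progression is meant.** Three features of the SAP favour first progression.

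1. The preceding sentence already deals with men who have not progressed on subsequent therapy. A separate rule for men without such therapy adds something only if it refers to a different progression.
2. A man without subsequent therapy cannot progress on it.
3. Where the SAP means last contact, it refers to the date last known alive (5.2.2 for OS; Table 3 for prostate cancer-specific survival).

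**What the rule does on that reading.** Let L be the last scan without progression, T1 the first progression and C the last contact, with L < T1 < C. Consider men with no subsequent therapy by C.

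- Not progressed by C: censored at the last progression-free date. This is ordinary censoring.
- Progressed at T1, then died at D, with D ≤ C: event at D, all time counted.
- Progressed at T1, alive at C: censored at L. The interval from L to C is lost, although he was known to be event-free.

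Only the third group is mishandled. Removing these survivors while keeping the deaths raises the estimated hazard after progression and shortens estimated PFS2.

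**Size.** The documents give no PFS2 event count, power or rate, so there is no stated figure to reproduce. The borrowed design input, rPFS medians of 20 and 30 months, belongs to a calculation that does check. With HR 0.67, two-sided alpha 0.005 and 85% power, events = 4(2.807 + 1.036)²/(ln 0.67)² = 59.1/0.1604, or 369 after rounding up. The SAP says approximately 368.

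The simulation used 300 trials of 1,000 men per setting, with an unstratified Cox model.

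- *From the documents:* 1:1 allocation, 30 months' accrual, the rPFS medians, cut-off at 54 months, and scans every 4 cycles (4 × 28 = 112 days, about 3.68 months), so L falls 0 to 3.68 months before T1.
- *Assumed:* 10% of rPFS events are deaths; the hazard of death after progression is 0.034 per month (median ln 2/0.034 = 20.4 months); median time to progression on subsequent therapy is 10 months; an additional cut-off at 36 months; and the shares and delays in the table.

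Affected men are control/apalutamide. Hazard ratios run from last-contact censoring to the SAP rule.

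| Never treated | Mean delay, months (control/apalutamide) | Affected, month 36 | HR, month 36 | Affected, month 54 | HR, month 54 |
|---|---|---|---|---|---|
| 0% | 1/1 | 8/7 | 0.685 to 0.684 | 4/4 | 0.684 to 0.684 |
| 10% | 2/2 | 29/23 | 0.687 to 0.679 | 23/20 | 0.696 to 0.688 |
| 20% | 3/3 | 48/38 | 0.694 to 0.679 | 42/36 | 0.688 to 0.671 |
| 40% | 3/3 | 72/56 | 0.693 to 0.665 | 71/60 | 0.692 to 0.659 |
| 20% | 2/6 | 42/50 | 0.632 to 0.630 | 37/46 | 0.644 to 0.636 |
| 20% | 6/2 | 63/33 | 0.772 to 0.738 | 51/33 | 0.743 to 0.718 |

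- Affected men range from about 8 (4.3 + 4.0) to 130 (70.6 + 59.5) of 1,000. Event-free men who have not progressed number about 342 to 567. The affected share is therefore 8.4/(8.4 + 343.0) = 2% to 130.2/(130.2 + 342.5) = 28% of event-free men not on subsequent therapy.
- Affected men lose a mean of 2.8 to 18.7 months of known event-free follow-up.
- At month 54 the control median PFS2 shortens by 0 to 3 months (largest: 36.3 to 33.2).
- In the 40% setting at month 54 the log hazard ratio moves by ln(0.692/0.659) = 0.049. With 466 simulated events the standard error is about 2/√466 = 0.093, so the shift is about half a standard error.

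A second simulation used a month-32 cut-off, delays of 2 to 6 months and 10 to 25% never treated. It assumed medians of 12 months to progression on next therapy and 22 months from first progression to death. It gave the same direction: 0.694 to 0.686, 0.679 to 0.663 and 0.673 to 0.648.

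**The case against.** The strongest reply is that the sentence does not say first progression. Elsewhere in Table 3, generic wording refers to the row's own event: in the row for symptomatic local progression, not having progressed plainly means not having progressed locally. Read that way, a man without subsequent therapy can be censored at last contact and the problem disappears. The general rule in Protocol 11.3 does not settle the matter, because it speaks of radiographic progression, does not fit OS and defers to the SAP. This objection stands in part. It makes the point conditional, but it does not rescue the sentence, since two programmers could derive different dates from it.

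Two stronger readings are tempting, and the documents support neither. A reader might infer that the rule mishandles everyone not on subsequent therapy. It does not: most event-free men in that group have not progressed, and death is an event whether or not therapy was started. A reader might also infer that the hazard ratio is materially biased. The rate and timing of subsequent therapy are not in the documents, and with short delays and no untreated men the shift is nil. Nor are more control men necessarily affected: with a longer delay on apalutamide, more apalutamide men are.

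It can also be said that SAP 5.1.2 leaves room for sensitivity analyses of censoring rules. That provision is permissive and does not name PFS2.

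**Conclusion.** The point holds conditionally. If progression in the second censoring sentence means first progression, PFS2 censoring is informative for men alive after first progression who have not started subsequent therapy. Sections 9.1.3 and 10.2 of the protocol make such men possible by design. If it means the PFS2 progression, there is no bias, but the term still needs defining.

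Under the assumptions listed, the hazard ratio moves by 0.00 to about 0.03. It moved towards apalutamide or not at all in every setting run; larger differences between arms in delay were not tried. These figures illustrate the mechanism and are not estimates for this trial. PFS2 is among the Other endpoints, outside the rPFS/OS alpha split and the SAP 5.3 condition for claiming secondary endpoints, so no primary or secondary conclusion depends on it. This is a minor correction.

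**What to change.** Replace the two PFS2 censoring sentences in SAP Table 3 with one rule: *A subject with no PFS2 event, whether or not subsequent therapy has started, is censored at the latest date he is known to be alive and free of progression on a first subsequent therapy. Death without subsequent therapy is an event.*

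If the sponsor wants to keep the present rule, it can be a sensitivity analysis with progression defined.

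The cost is a short SAP text change and the matching derivation. No new data are needed: survival, first subsequent therapy and progression on it are already collected in follow-up, and men still on study drug are seen at treatment visits.
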